This form will be completed at the end of the gastrostomy procedure, either by the local champion or the member of the team performing the gastrostomy insertion. The form is designed to capture the details of the procedure with regard to staffing; gastrostomy equipment; drugs given; patient monitoring and respiratory support; as well as, any complications that occur during the procedure.

iv) 3-month Follow Up Patient Evaluation Form (see Appendix 4)

This form is designed to capture data with regard to gastrostomy complications occurred prior to patient's hospital discharge and those occurred after the hospital discharge up to the 3-month patient evaluation. Weight and ALSFRS-R for each patient will also be recorded. This form will be completed by the local champion after a patient's usual follow up visit which coincides nearest with 3 months post gastrostomy.

v) 12-month Follow Up Patient Evaluation Form (see Appendix 5)

This form is designed to capture data with regard to gastrostomy complications occurred in the period of time between the 3-month patient evaluation and the 12-month patient evaluation. Weight and ALSFRS-R for each patient will also be recorded. This form will be completed by the local champion after a patient's usual follow up visit which coincides nearest with 12 months post gastrostomy.

vi) McGill Quality of Life Questionnaire (MQOL) (see Appendix 7)

This is a well-established questionnaire, designed in the context of palliative care, to identify the health-related quality of life of patients with a terminal illness. It balances physical and non-physical aspects of quality of life, and includes both positive and negative influences on quality of life [53]. This questionnaire will be completed by patients at baseline and at 3 months post gastrostomy.

vii) Modified Caregiver Strain Index (MCSI) (see Appendix 8)

This is a well-established questionnaire, designed to identify the strain levels among informal carers of patients with long-term illness. It will be used in this study to assess the quality of life of the main carer of the patient and the impact that the treatment is having on the carer [54]. It will be completed by carers at baseline and at 3 months post gastrostomy.

viii) Gastrostomy-specific questionnaire (Gastro-Qu) (see Appendix 9)

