7.7 Data Analysis

Quantitative data analysis

All quantitative data will be managed and analysed using SPSS for Windows version 14.0 (SPSS Inc., 1998). Exploratory data analysis will be initially carried out to establish the distribution of all continuous and categorical variables. Descriptive statistics (means, standard deviations, percentages) will be used to describe the characteristics of the participating centres, the participants and all the main variables of the study. Non-parametric tests (Spearman rank correlation tests and Mann Whitney U tests) will be performed for non-normally distributed continuous variables. Cronbach's alpha (α) coefficients will be determined for the measures that will be used in the study (i.e., MQOL, MCSI, gastrostomy questionnaire) in order to establish their internal consistency.

Continuity corrected Chi-square (χ^2) tests will be performed to determine the difference in the first-month mortality rate and the complication rate following gastrostomy in PEG and PIG/RIG patients. The same tests will be also performed to determine the self-perceived quality of life changes following gastrostomy in PEG and PIG/RIG patients as well as to determine the changes in carer quality of life. Kaplan-Meier survival curves will be used to determine the median survival time from placement of feeding tube, symptom onset and time of diagnosis of the disease in PEG and PIG/RIG patients. Independent samples t-tests will be used to determine the nutritional status changes following gastrostomy in PEG and PIG/RIG patients. Predictors of survival (e.g., respiratory status, site of symptom onset, stage of disease) following gastrostomy will be determined using logistic regression analysis and Cox proportional hazards regressions analysis.

Qualitative data analysis

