PIG is a hybrid technique in which the stomach is punctured under fluoroscopic guidance, following which the oesophagus is catheterised in a retrograde fashion using a guide wire. A gastrostomy tube is then passed over the guide wire at the mouth end, down the oesophagus and out through the abdominal wall. Conscious sedation is used, usually with a combination of midazolam with either pethidine or fentanyl.

Variation at your centre (please, use the space below)

.....

.....

.....

.....

.....

Please add any other comments that you may have with regard to this study in the space provided.

.....

.....

.....

.....

.....

.....

.....

Please return to:

[name], Academic Neurology Unit, University of Sheffield,
[name]

Pre Gastrostomy Patient Evaluation

Coded participant number: _____

Date of evaluation: _____

Date referred for gastrostomy: _____

Age: _____ **Gender:** (please tick) Female Male

Date of onset of MND symptoms (weakness): _____

Date of MND diagnosis: _____

Date of first contact by MND Centre: _____

MND site of onset: (please tick) Limb Bulbar

Weight (Kg) _____ **Height (m)** _____

Weight at diagnosis or earliest previous recorded weight since MND diagnosis:

Weight (Kg) _____ **Date** _____

Most recent respiratory assessment: (please, as complete as possible)

FVC % _____ **SNIP** _____

Most recent gases (arterial or transcutaneous): Date recorded _____

pO2 _____ **pCO2** _____ **O2 sats** _____

Indication for gastrostomy: (please, tick any that apply)

Marked weight loss

Unsafe swallow

Recurrent aspiration

Prolonged and difficult meals

Other _____

What do you think the benefits of gastrostomy will be for this patient? *(please, tick Yes or No for each of the options provided)*

	Yes	No
Prolong survival		
Stabilise nutrition and hydration		
Reduce risk of choking		
Reduce risk of chest infection		
Reduce risk/prevent aspiration		
Ease the difficulties of feeding (e.g. anxiety)		
Alternative route for medication		
Improve quality of life		

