Reduce carer burden		
Other _____		

Preferred Gastrostomy procedure for this patient: *(please tick)*

PEG PIG RIG Surgical
 Other _____

Why was this method selected for this patient? *(please, use the space provided)*

.....

Has the patient's perception of gastrostomy influenced the timing or any other aspect of dysphagia management? *(please tick)*

Yes No

▪ If yes, please detail how in the space provided:

.....

Important Note

Please issue the MQOL questionnaire to the patient and the MCSI to the carer. These must be completed by the participants before the gastrostomy placement.

Peri-Procedure Patient Evaluation

Coded participant number: _____

Date of hospital admittance: _____

Clinic: _____

Date of Procedure: _____

Type of Gastrostomy : _____

Staffing: *(please, tick if present)*

Anaesthetist Anaesthetic assistant Radiologist

Radiographer Endoscopist Nurse

Other _____

Patient pre procedure: O₂ sats _____ pCO₂ _____

Drugs given for gastrostomy:

Name	Amount	Indication
1		
2		
3		
4		
5		

Monitoring: *(please, tick those performed through procedure and record most abnormal value)*

Heart rate _____ BP _____ Respiratory Rate _____

O₂ Sats _____ CO₂ _____

Respiratory support: *(please tick)*

Does patient use NIV routinely? Yes No

Was NIV used during the gastrostomy? Yes No

Was supplementary oxygen given? Yes No

Gastrostomy equipment:

Tube product number/type _____

Tube size _____

Tube manufacturer _____

Complications:

Duration of procedure _____

Was this a difficult gastrostomy? *(please, tick)* Yes No

Indicate complications: *(please, tick any that apply)*

Desaturation Respiratory arrest Laryngeal spasm

Patient distress Failure to complete Haemorrhage

Please, detail other complications or notable issues relating to this gastrostomy procedure
(please, use the space provided):

.....

.....

.....

.....

.....

3 Month Follow Up Patient Evaluation

Coded participant number: _____

Date of evaluation: _____

Date of discharge after gastrostomy: _____

Weight (Kg): _____

Complications following Gastrostomy: *(please, tick any that apply for complications that have occurred since gastrostomy insertion)*

	Prior to Discharge	After Discharge
Tube blockage		
Tube displacement		
Tube leakage		

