Infection		
Granulation tissue		
Pain		
Gastric haemorrhage		
Perforation		
Peritonitis		
Pneumonia		
Increased anxiety		
Nausea		
Diarrhoea		
Constipation		
Fatigue		

Please, state how these complications were managed: *(please, use the space provided)*

.....

.....

.....

.....

.....

Repeat gastrostomy required: (please, tick) Yes No

If yes,

- Reason _____
- Method used for 2nd procedure _____

Bedside tube replacement required: (please, tick) Yes No

If yes,

- Reason _____

If patient dead:

- Date of Death _____
- Cause of Death _____
- Was cause of death directly related to Gastrostomy procedure? *(please tick)*
Yes No Uncertain

- If available record the value and date of the last post procedure weight:

Weight (Kg) _____ Date recorded _____

Please detail other complications or notable issues relating to this gastrostomy procedure:
(please, use the space provided)

.....
.....
.....
.....
.....
.....
.....

Important Note

Please issue the MQOL and Gastro-Qu questionnaires to the patient and the MCSI to the carer. These must be completed by the participants approximately at 3 months following gastrostomy.

12 Month Follow Up Patient Evaluation

Coded participant number: _____

Date of evaluation: _____

Weight (Kg): _____

Complications following Gastrostomy: *(please, tick any that apply for complications that have occurred since the 3 month follow up visit)*

- | | | | | | |
|---------------------|--------------------------|--------------------|--------------------------|--------------|--------------------------|
| Tube blockage |  | Tube displacement |  | Tube leakage |  |
| Infection |  | Granulation tissue |  | Pain |  |

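### Complications are recorded only as positive ticks, so the forms alone cannot tell absent from not asked or not known, and uneven completion between centres can bias the PEG v PIG/RIG complication comparison

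*Protocol*

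**What the plan says.** Protocol section 7.5 lists the difference in complication rate between PEG and PIG/RIG as the first secondary outcome, and section 4 (vi) states the matching hypothesis. Section 7.7 assigns the continuity-corrected chi-square test to "the first-month mortality rate and the complication rate following gastrostomy in PEG and PIG/RIG patients".

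The data come from three forms:

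- **Peri-procedure form (Appendix 3):** six named complications, headed "please, tick any that apply".
- **3-month form (Appendix 4):** fifteen complications, headed "please, tick any that apply for complications that have occurred since gastrostomy insertion". The two columns, "Prior to Discharge" and its after-discharge counterpart, record timing only.
- **12-month form (Appendix 5):** the same fifteen complications with one box each, headed "please, tick any that apply for complications that have occurred since the 3 month follow up visit".

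None of the lists offers No, None or Not known. Other items do have an explicit negative. The follow-up forms ask "Repeat gastrostomy required: (please, tick) Yes No", with the same layout for bedside tube replacement. The expected-benefits question on the pre-gastrostomy form (Appendix 2) asks the clinician "please, tick Yes or No for each of the options provided".

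Of each follow-up form, section 7.2 says "This form will be completed by the local champion after a patient's usual follow up visit". Section 7.6 says that most centres perform only one type of procedure. Section 8.2 makes the evaluation forms source data and describes a check of the central copies against the forms held at the sites.

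**The concern.** A positive-tick list gives the same blank for three different facts: the complication did not occur, nobody asked, or the answer was not known. If blanks are read as no complication, the recorded rate falls as completion becomes less thorough.

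That would matter less if completion were unrelated to method. Here each centre's own staff fill in the forms and most centres use a single method, so a difference in diligence between centres is largely carried into the method comparison. The method used at the more careful centres would look worse. The check in section 8.2 cannot detect this, because a photocopy reproduces the blank.

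At stake is a named secondary outcome that is meant to inform guidance on insertion method. One-month mortality rests on the date of death and does not use these lists.

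**Working it through.** The protocol gives no figure to reproduce on this point: it states neither an expected complication rate nor a completion rate. The calculation below is an illustration.

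**Inputs**
- Recruitment of 504 (section 7.6). An equal split, 504 / 2 = 252 per group, is an assumption; the protocol states none.
- Test: continuity-corrected chi-square (section 7.7), two-sided 5%.
- True complication rate p, the same with both methods: assumed 30%, with 20%, 10% and 5% as variants.
- Fraction b of patients whose list was not asked and left blank, by group: assumed. Blanks are taken to be unrelated to whether a complication occurred.

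**Formulas**
- Observed rate = p × (1 − b). For example, 0.30 × (1 − 0.15) = 0.255.
- For x₁ and x₂ ticked patients out of n = 252 each, with N = 504 and m = x₁ + x₂: X² = N × (|x₁(n − x₂) − x₂(n − x₁)| − N/2)² / (n × n × m × (N − m)). Reject if X² > 3.841.
- Rejection probability = the sum, over all (x₁, x₂) that reject, of the product of the two binomial probabilities at the observed rates (exact enumeration).

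**Results**

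| True rate, both methods | Blank, group A v B | Observed rates | Test rejects in |
|---|---|---|---|
| 30% | 0% v 0% | 30% v 30% | 4.0% |
| 30% | 15% v 15% | 25.5% v 25.5% | 3.9% |
| 30% | 10% v 15% | 27% v 25.5% | 5.4% |
| 30% | 5% v 15% | 28.5% v 25.5% | about 10% |
| 30% | 0% v 15% | 30% v 25.5% | 17.8% |
| 30% | 0% v 20% | 30% v 24% | 29.5% |
| 20% | 0% v 20% | 20% v 16% | 18.5% |
| 10% | 0% v 15% | 10% v 8.5% | 6.5% |
| 10% | 0% v 20% | 10% v 8% | 9.2% |
| 5% | 0% v 20% | 5% v 4% | 5.6% |

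The reference is about 4% and not 5%, because the continuity correction makes the test conservative.

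Three things follow. Equal blanking in both groups lowers the rates but does not raise false rejection. The excess depends on the difference in blanking between methods. The excess shrinks quickly as the complication becomes rarer.

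**The case against.** **Is this only form style?** A prompted tick list is an ordinary layout, and the protocol does not contradict itself by using one: gastrostomy indication on the pre-gastrostomy form, also a factual item, is collected the same way. That stands. The point is what a blank can mean for an outcome variable, not inconsistency between forms.

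**Can blanks be resolved later?** A reader might infer that nothing could ever separate the meanings of a blank. The document does not support that:
- Section 8.2 also calls the medical notes source data, with consent for access and 15-year retention, so a doubtful blank can be queried.
- The Yes/No items on the same follow-up forms help to identify a form that was not completed at all.
- Deaths have their own block on those forms.
- At 3 months the patient-completed Gastro-Qu grades pain, leakage, blockage, bleeding, infection and falling out, with an explicit lowest category.

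These are partial remedies. No routine check of complications against the notes is described. Gastro-Qu reaches only survivors who return it, and it omits perforation, peritonitis and pneumonia. What stands is that the forms alone cannot separate the meanings.

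**Does the mechanism fit all three forms?** Not equally. The peri-procedure form is filled in at the end of the procedure by the local champion or a member of the procedural team, and most of its items need no patient interview. On the follow-up forms the printed list is itself a prompt, and serious events are less likely to be missed because nobody asked. The protocol does not show that unasked items will be frequent, only that they could not be seen.

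**Is the size a worst case?** The rows with no blanks in one group are one-sided. With each method spread over several sites, smaller contrasts are plausible, and at 10% v 15% the excess is slight.

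**Conclusion.** The point holds as a limited one. All three complication lists lack a negative or not-known response, and most centres use one method, so uneven completion can bias the PEG v PIG/RIG complication comparison. The planned copy-against-copy check would not reveal it.

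The risk is mainly on the two follow-up forms and for common complications. At an assumed true rate of 30%, false rejection ranges from about 5% (10% v 15% blank) through 10% (5% v 15%) to 18% (0% v 15%), against 4% without blanks. At a true rate of 10% it reaches only 6.5% with 0% v 15%. The true rates, the blank fractions and the equal split are all assumptions.

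A reader might infer that the complication comparison will be biased, or that the study's main conclusion is threatened. Neither is supported: the protocol gives no completion rates, and the primary outcome does not use these lists. This is a cheap improvement to how a secondary outcome is recorded.

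**What to change.** 1. **3-month and 12-month forms:** give each complication Yes / No / Not known, with an instruction to answer every line. On the 3-month form, keep the prior-to and after-discharge boxes as timing for a Yes.
2. **Peri-procedure form:** at least add a none-of-these box, so that a reviewed list with no events differs from a skipped one.
3. **Queries:** check blank or Not-known items against the medical notes.
4. **Reporting:** give the Not-known fraction by method and by centre. Show each complication rate three ways: among Yes/No answers, with Not known counted as No, and with Not known counted as Yes. The first alone is not enough, because Not known may be concentrated in patients who died or were too ill to attend, and dropping them could remove the sickest.

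As an example of what this would show, take the assumed 30% true rate with 15% Not known in one group. That group has 25.5% Yes, 59.5% No and 15% Not known. The three rates are 25.5 / 85 = 30%, 25.5%, and 25.5 + 15 = 40.5%, so the dependence on the unknown answers is plain.

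**Cost:** re-layout of three forms, ideally before first use, and some query work. The 3-month list grows from 15 × 2 = 30 boxes to 15 × (3 + 2) = 75. No new assessments or visits are needed. The change makes uneven ascertainment visible but does not remove all centre-by-method confounding: a centre can still tick No down the column without asking.
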